12.5. Primary Analysis

A maximum of 30 evaluable subjects with soft tissue sarcoma will be enrolled as a single cohort. It is not anticipated that the addition of pembrolizumab to standard chemotherapy will increase the rate of severe or life-threatening toxicity. It has been reported that the rate of any severe or life-threatening toxicity of doxorubicin and dacarbazine every 3 weeks is 55%⁴⁸.

If it becomes evident that the rate of severe or life-threatening toxicity convincingly exceeds 55%, enrollment to the study will be halted.

The stopping rule will hold enrollment if the posterior probability of severe or life-threatening toxicity risk exceeding 0.55 is 75% or higher. In this event, data will be evaluated to inform the subsequent conduct of the study. The prior for this monitoring rule is beta (11,9). This means that our prior assumption regarding the proportion of severe or life-threatening toxicity is 0.55, and there is 90% probability that this proportion is between 0.368 and 0.726. The operating characteristics of the stopping rule are given in Table 11 and are based on 5000 simulations:

Table 11. Operating characteristics of the stopping rule

Number of Subjects with Severe or Life-Threatening Toxicities	Max. Denominator Cutoff for Early Stopping	Posterior Probability: $\Pr(\text{Risk} > 0.55 \text{Data})$
4	4	0.7834
5	6	0.7536
6	7	0.8056
7	9	0.7728
8	11	0.7694
9	13	0.7558
10	14	0.7944
11	16	0.7812
12	18	0.7592
13	19	0.8002
14	21	0.7818
15	23	0.7710
16	25	0.7594
17	26	0.7988
18	28	0.7828
19	30	0.7706

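### Table 11 orders an enrollment hold at 9 toxicities in 13 subjects, where the exact posterior is 0.7488 and the stated 75% rule says continue

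*Combined protocol and SAP*

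**What the plan says.** Section 12.5 (Primary Analysis) defines the monitoring rule through a Beta(11,9) prior, a reference rate of 0.55 and an inclusive threshold: "The stopping rule will hold enrollment if the posterior probability of severe or life-threatening toxicity risk exceeding 0.55 is 75% or higher". It describes the prior as centred on 0.55 and adds that "there is 90% probability that this proportion is between 0.368 and 0.726". On the sample size it says "A maximum of 30 evaluable subjects with soft tissue sarcoma will be enrolled as a single cohort".

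Table 11 in the same section lists, for 4 to 19 toxicities, the largest number of subjects at which a hold is triggered, together with the posterior probability at that point. The text says that the table's figures "are based on 5000 simulations". The row for 9 toxicities gives a denominator of 13 and a posterior of 0.7558.

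Section 12.4.1 says that the rule is assessed continuously. Section 12.1 bases the sample size on it.

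**The concern.** The prior, the reference rate and the threshold together fix every boundary exactly, so Table 11 should follow from the text with nothing left to chance. At 9 toxicities in 13 subjects it does not: the text, evaluated exactly, says continue, and the table says hold.

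The toxicity rate is the primary objective (Section 1.1), and Table 11 is the only boundary table in the plan. Staff reading the table and a statistician computing the posterior would reach opposite answers on the same data, and nothing in the plan says which of the two governs.

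**Working it through.** **Inputs (all from Section 12.5).** Prior Beta(11,9); hold if Pr(rate > 0.55 | data) ≥ 0.75; maximum of 30 subjects; Table 11 row for 9 toxicities: denominator 13, posterior 0.7558.

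**Prior check.** The 5th and 95th percentiles of Beta(11,9) are 0.3681 and 0.7261, and the mean is 11/20 = 0.55. Both agree with the text, so the prior has been read correctly.

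**Formula.** With x toxicities in n subjects the posterior is Beta(A, B), where A = 11 + x and B = 9 + n − x. Then

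Pr(rate > 0.55) = Pr(Binomial(A + B − 1, 0.55) ≤ A − 1).

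This is exact and needs no simulation.

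**The disputed row.**

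| Data | Posterior | Pr(rate > 0.55) | Stated rule | Table 11 |
|---|---|---|---|---|
| 9/12 | Beta(20,12) | 0.8113 | hold | hold |
| 9/13 | Beta(20,13) | 0.7488 | continue | hold (prints 0.7558) |
| 10/13 | Beta(21,12) | 0.8487 | hold | hold |

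So the largest denominator that triggers a hold with 9 toxicities is 12. With 13 subjects, a hold needs 10 toxicities.

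**The other rows.** For each number of toxicities, the largest n with a posterior of at least 0.75 was found. The other 15 denominators in Table 11 reproduce. For every n from 1 to 30, table and rule require the same number of toxicities, except at n = 13 (table 9, rule 10).

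**Could another prior explain 0.7558?** For 9/13, neighbouring priors give 0.680 for Beta(11,10), 0.698 for Beta(10,9), 0.794 for Beta(12,9) and 0.811 for Beta(11,8). None matches.

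**Likely cause.** All 16 printed posteriors are whole multiples of 1/5000 (0.7558 = 3779/5000), as expected if each is a proportion of 5000 draws. At 9/13 the Monte Carlo standard error is √(0.7488 × 0.2512 / 5000) = 0.0061. The printed value is 0.7558 − 0.7488 = 0.0070 too high, or 1.1 standard errors. The exact value is only 0.0012 below the threshold, so ordinary noise is enough to cross it: in repeated runs of 5000 draws from Beta(20,13), 40% to 45% came out at 0.75 or more. The largest deviation is at 7/9 (printed 0.7728, exact 0.7865, difference 0.0137), but that cutoff is unaffected.

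**Effect on the trial.** These are exact recursions, with the rule assessed after every subject up to 30.

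| True rate | First meets the table's boundary at 9/13 | Ever held: exact rule | Ever held: Table 11 |
|---|---|---|---|
| 0.50 | 2.9% | 27.7% | 28.4% |
| 0.55 | 4.6% | 43.8% | 44.6% |
| 0.60 | 6.2% | 62.2% | 62.9% |
| 0.65 | 7.5% | 79.2% | 79.6% |

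The net change is smaller than the first-crossing probability because most trials that pass through 9/13 would later be held under the exact rule as well: 76%, 83%, 90% and 95% of them at the four rates.

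**The case against.** The strongest reply is that the discrepancy is trivial in practice. It concerns one row and one sample size. The shortfall is 0.0012, and 0.7488 is 75% when rounded to a whole percent, the precision in which the rule is worded. The plan discloses that the figures were simulated. The error brings a hold forward and never delays one, and a hold leads to a review of the data, not to termination. The overall hold probability moves by less than one percentage point. The endpoint carries far more discretion than this: Section 12.2.1 counts an event only if the Sponsor-Investigator judges it related and important enough to count, and reclassifying one subject from 9/13 to 10/13 moves the posterior by 0.8487 − 0.7488 = 0.0999.

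All of this is true, and it limits the practical weight of the point. It does not remove the contradiction. The plan gives no rounding rule and the table works to four decimals, so rounding cannot be assumed to reconcile the two. Disclosing the simulation explains the error but does not correct the boundary. The inaccurate posteriors in the other rows change no decision, and replacing them is only tidying that comes free with the recalculation.

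**Conclusion.** The point holds. Under the plan's own prior and threshold, 9 toxicities in 13 subjects gives 0.7488 and does not meet the hold criterion; Table 11 says that it does. It is the only point up to 30 subjects at which table and rule differ.

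The chance of first meeting the table's boundary there is 2.9% to 7.5% for true rates of 0.50 to 0.65. The net effect on the overall hold probability is 0.4 to 0.8 percentage points, in the cautious direction. These probabilities assume assessment after every subject, independent outcomes with a constant rate, and no rounding of the posterior before it is compared with 75%.

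The correction is needed because the decision table for the primary safety rule contradicts the rule itself. The effect on the design's operating characteristics is small.

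**What to change.** Recompute Table 11 from the exact beta distribution function. Change the row for 9 toxicities to a maximum denominator of 12 with posterior 0.8113, replace the remaining simulated posteriors with exact values, and remove the statement about 5000 simulations for that column. The other 15 denominators stay as they are.

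If the sponsor does intend a hold at 9/13, the text must say that the table governs there, because the stated 75% rule does not produce it.

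The work is one replaced table and a few words of text, with no change to the sample size, the prior or the threshold. Because it alters a monitoring boundary, it goes through the modification process in Section 16.1 (agreement with the drug supplier, and IRB approval of the amendment where required).

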I. Statistical Analysis	Previous reports have demonstrated that the rate of any severe or life-threatening toxicity with a median of 3 courses of doxorubicin and dacarbazine every 3 weeks is 55%. If it becomes evident that the rate of severe or life-

	
threatening toxicity convincingly exceeds 55%, the study will be halted. Response rates will be calculated with corresponding 95% confidence intervals based on the Clopper-Pearson method. Duration of response and PFS distributions will be estimated using Kaplan-Meier techniques. Exploratory correlative analyses will be conducted on biomarkers using logistic regression (response rate) and Cox proportional hazards models (duration of response and PFS). Incident rates for adverse events, SAEs, and deaths on study therapy will be summarized.

--	--

SCHEMA

* Subjects 12-17 years of age will receive pembrolizumab 2 mg/kg IV (up to 200 mg) every 3 weeks

LIST OF ABBREVIATIONS

Abbreviation	Definition of Term
AE	Adverse event
ALT	Alanine aminotransferase
aPTT	Activated partial thromboplastin time
AST	Aspartate aminotransferase
CI	Confidence interval
CHF	Congestive heart failure
CFR	Code of Federal Regulations
CNS	Central nervous system
CR	Complete response
CT	Computed tomography
CTCAE	Common Terminology Criteria for Adverse Events
CTMS	Clinical trial management system
CrCl	Creatinine clearance
DCSI	Development Core Safety Information
DNA	Deoxyribonucleic acid
DSMC	Data and Safety Monitoring Committee
eCRF	Electronic case report form
ECG	Electrocardiogram
ECI	Events of clinical interest
ECHO	Echocardiogram
ECOG	Eastern Cooperative Oncology Group
FDA	Food and Drug Administration
FSH	Follicle-stimulating hormone
GCP	Good Clinical Practice

G-CSF	Granulocyte-colony stimulating factor
GIST	Gastrointestinal stromal tumor
GMP	Good Manufacturing Practices
HIV	Human immunodeficiency virus
IB	Investigator brochure
IDS	Investigational drug services
IHC	Immunohistochemistry
INR	International normalized ratio
IRB	Institutional Review Board
irRC	Immune related response criteria
IV	Intravenous
LCI	Levine Cancer Institute
LVEF	Left ventricular ejection fraction
mAb	Monoclonal antibody
MEL	Melanoma
MRI	Magnetic resonance imaging
MUGA	Multigated acquisition scan
NSCLC	Non-small cell lung cancer
ORR	Objective response rate
OTC	Over the counter
PI	Principal Investigator
PK	Pharmacokinetics
PR	Partial response
PT	Partial thromboplastin
Q2W	Every two weeks
Q3W	Every three weeks
RCC	Renal cell carcinoma

RNA	Ribonucleic acid

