12. STATISTICAL CONSIDERATIONS

12.1. Sample Size

This study is primarily designed to assess the safety of doxorubicin (60-75 mg/m²) and pembrolizumab (200 mg) in previously treated or untreated subjects with

unresectable or metastatic soft tissue sarcoma. Based on the Bayesian stopping rules described in Section 12.5, 30 subjects will enable an assessment regarding whether or not the severe or life-threatening treatment emergent adverse event rate convincingly exceeds 0.55.⁴⁸

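### Table 11 gives the stopping boundary, not the operating characteristics Section 12.5 says it gives; the boundary would be crossed in about 44% of trials at a true rate of exactly 55%

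*Combined protocol and SAP*

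**What the plan says.** Section 12.5 takes its benchmark from a cited report: "the rate of any severe or life-threatening toxicity of doxorubicin and dacarbazine every 3 weeks is 55" per cent. The prior is Beta(11,9), described by its mean of 0.55 and by the statement that "there is 90% probability that this proportion is between 0.368 and 0.726". The trigger is: "The stopping rule will hold enrollment if the posterior probability of severe or life-threatening toxicity risk exceeding 0.55 is 75% or higher". A data review is to follow and to guide how the study goes on. Section 12.5 then introduces the table: "The operating characteristics of the stopping rule are given in Table 11 and are based on 5000 simulations".

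Table 11 has three columns: the number of subjects with a qualifying toxicity, the largest denominator at which that number stops the trial, and the posterior probability at that point. Its 16 rows run from 4/4 to 19/30.

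Section 12.1 rests the sample size on this rule alone: "30 subjects will enable an assessment regarding whether or not the severe or life-threatening treatment emergent adverse event rate convincingly exceeds 0.55". Section 12.4.1 says the rule is assessed continuously, and Section 12.9 refers back to that.

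The consequence of crossing varies. The synopsis (item I) says that if the rate of "threatening toxicity convincingly exceeds 55%, the study will be halted". Section 12.5 says first that "enrollment to the study will be halted" and then describes a hold with data review.

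**The concern.** Operating characteristics are probabilities of what a rule does under assumed true rates: how often it fires, how early, and how often it misses. Table 11 assumes no true rate and contains none of these, and they appear nowhere else in the plan. A committee reading Section 12.5 would believe this had been examined and could not see how often the rule fires at the rate the plan itself expects. Section 12.5 anticipates no rise over standard chemotherapy.

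The gap matters because the primary objective is the toxicity rate against historical control, and the rule is the only argument offered for 30 subjects. If it fires often at exactly 55%, crossing it cannot bear the weight of the word 'convincingly', and a reader may also over-interpret a trial that never crosses.

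**Working it through.** **Inputs.** From Section 12.5: prior Beta(11,9), benchmark 0.55, threshold 0.75, maximum 30 subjects. From Section 12.4.1: continuous assessment, modelled here as a look after each subject. Assumption: each subject's outcome is known before the next is counted.

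**1. The plan's prior.** The mean is 11/(11+9) = 0.55. The 5th and 95th percentiles of Beta(11,9) are 0.3681 and 0.7261, which match the printed interval. The prior already gives Pr(risk > 0.55) = 0.506, so a hold needs a rise from 0.506 to 0.75.

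**2. The plan's boundary.** After x toxicities in n subjects the posterior is Beta(11+x, 9+n−x), and the rule fires when Pr(Beta(11+x, 9+n−x) > 0.55) ≥ 0.75.

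| Row | Posterior | Exact Pr(risk > 0.55) | Printed |
|---|---|---|---|
| 4/4 | Beta(15,9) | 0.7797 | 0.7834 |
| 7/9 | Beta(18,11) | 0.7865 | 0.7728 |
| 9/13 | Beta(20,13) | 0.7488 | 0.7558 |
| 19/30 | Beta(30,20) | 0.7671 | 0.7706 |

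Fifteen of the 16 cutoffs agree with the exact rule. Row 9/13 does not: 0.7488 is below 0.75, and the exact cutoff for 9 events is 12. The largest difference between printed and exact posteriors is 0.0137 (row 7/9). The Monte Carlo standard error of 5000 draws there is √(0.7865 × 0.2135 / 5000) = 0.0058. Differences of this size suggest that the 5000 simulations were draws from the posterior rather than simulated trials. That is an inference; the plan does not say.

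**3. The missing operating characteristics.** Let a(n,k) be the probability of reaching n subjects with k toxicities and no earlier crossing, for true rate p. Then a(n,k) = (1−p)·a(n−1,k) + p·a(n−1,k−1). After each n, every cell that meets the rule is removed and added to the crossing probability. The expected number enrolled is Σ n·P(first crossing at n) + 30·P(no crossing).

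Check on the first step: 3/3 gives a posterior of 0.7236, so no crossing is possible before n = 4. At p = 0.55 the chance of crossing at 4/4 is 0.55⁴ = 0.0915.

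| True rate | P(boundary crossed by n = 30) | Expected number enrolled at first crossing (or 30) |
|---|---|---|
| 0.40 | 8.4% | 28.2 |
| 0.45 | 15.9% | 26.8 |
| 0.50 | 27.7% | 24.8 |
| 0.55 | 43.8% | 22.1 |
| 0.60 | 62.2% | 18.8 |
| 0.65 | 79.2% | 15.3 |
| 0.70 | 91.2% | 12.1 |
| 0.75 | 97.4% | 9.4 |

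These figures follow the exact 0.75 rule. With the printed cutoffs, including 9/13, the values at 0.55 are 44.6% and 21.8 enrolled; a 5000-trial simulation of the printed cutoffs gave 45.0%. A crossing at n = 30 leaves no enrollment to hold. Leaving out that look lowers the printed-cutoff figure from 44.6% to 43.2%.

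**4. Sensitivity to the look schedule, true rate 0.55.**

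| Looks | P(boundary crossed) |
|---|---|
| After each subject | 43.8% |
| Every 5 subjects | 33.8% |
| Every 10 subjects | 28.5% |
| At n = 30 only | 23.3% |

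**5. What not crossing means.** With 18/30 the posterior is Beta(29,21), with mean 29/50 = 0.58 and Pr(risk > 0.55) = 0.67. The trial finishes without a hold although the posterior still favours a rate above 55%.

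**The case against.** A sensitive trigger is a legitimate choice for a safety rule, and a Bayesian rule need not control a type I error rate. Prior, threshold and action are all stated, and apart from row 9/13 the rule can be run as written. This stands, and it is why neither the threshold nor the sample size is criticised here. For the same reason it would not be fair to fault the rule because a 95% confidence interval for 19/30 includes 55%: the plan never adopted that test.

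A reader might infer that the trial would be terminated in 44% of cases at the benchmark rate. The documents do not support that. Section 12.5 describes a hold and a data review, after which enrollment might resume, so 44% is the chance of crossing and the expected numbers are counts at first crossing, not final sample sizes. A reader might also infer that a crossing would be published as proof of excess toxicity. The plan nowhere says so.

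The 44% rests on a look after every subject. Continuous assessment supports frequent looks, but the schedule is not fixed, and sparser looks give 23% to 34%.

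Finally, 55% may not be the rate to expect for the event counted. Section 12.2.1 requires it to be serious, drug-related and judged clinically significant enough to count towards the rule. That may be narrower than the toxicity in the cited report, and the plan gives no expected rate for it. If the true rate is lower, the chance of a hold falls quickly, to 15.9% at 0.45 and 8.4% at 0.40. This is a reason to print the whole table, not one figure.

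**Conclusion.** The point holds, as a should-fix. Table 11 is a stopping boundary; the operating characteristics that Section 12.5 says it contains are absent from the plan. With a look after each subject and immediate outcomes, the boundary is crossed in 43.8% of trials at a true rate of 55% and in 27.7% at 50%. With sparser looks the figure at 55% is still 23.3% to 33.8%. A rule that fires this often at the benchmark does not show that the rate convincingly exceeds it, so the property on which Section 12.1 rests the 30 subjects is not one the rule has. Nor does finishing without a crossing establish a rate of 55% or less.

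Row 9/13 contradicts the stated threshold. The effect is small (44.6% against 43.8% at 0.55), but it must be settled before any figures are printed. The synopsis and Section 12.5 also need reconciling on what a crossing leads to.

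**What to change.** 1. Rename Table 11 as the stopping boundary, compute its posteriors exactly, and settle row 9/13: either the cutoff becomes 9/12, or the printed cutoff is kept and declared an exception to the 0.75 rule.
2. Add an operating-characteristics table for the boundary finally adopted, giving for each true rate the probability of crossing and the expected number enrolled at first crossing. State the look schedule it assumes. The table in step 3 of the working serves if the exact rule and a look after each subject are adopted.
3. In the synopsis and Sections 12.1 and 12.5, replace the claim about convincingly exceeding 55% with: *posterior probability of at least 75%, a trigger for an enrollment hold and safety review*. Cite the new table, and state that not crossing does not establish a rate of 55% or less.
4. Reconcile the synopsis, which halts the study, with the hold and data review in Section 12.5, so that one consequence is stated throughout.
5. Report the final primary rate with its posterior mean, 95% credible interval and Pr(risk > 0.55).

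The cost is wording and one computed table, with no extra subjects and no change of threshold. The downside is that the stated properties of the design will look less favourable than the present text implies.

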12.6. Secondary Analyses

Response rates (based on RECIST 1.1 criteria) will be calculated with corresponding 95% confidence intervals based on the Clopper-Pearson method. The duration of response, overall survival, and progression free survival (PFS) distributions will be estimated using Kaplan-Meier techniques. Secondary correlative analyses will be conducted on baseline subject and disease characteristics, and selected biomarkers using logistic regression (response rate) and Cox proportional hazards models (duration of response, overall survival, and PFS).

12.7. Safety Analyses

Incident rates for adverse events, treatment-emergent adverse events, SAEs and deaths while on study therapy will be summarized. Treatment-emergent adverse events are defined as follows:

- An adverse event that occurs after treatment start that was not present at the time of treatment start; or
- An adverse event that increases in severity after treatment start if the event was present at the time of treatment start.

12.8. Exploratory Analyses

Analysis of objective response, duration of response, and PFS whereby the endpoints are based on irRECIST will be conducted using methods as described in Section 12.6. Correlative analysis will be conducted on PD-L1 and other biomarkers using logistic regression for objective response and Cox proportional hazards models for time to event endpoints. Other exploratory analysis will be conducted as deemed necessary. Summaries of second course objective response rate and progression free survival will be conducted.

12.9. Interim Analyses

This study will be continuously evaluated as described previously in Section 12.4.

13. STUDY COMPLETION

13.1. Completion

The study will be considered complete when one or more of the following conditions is met:

- All subjects have completed all study visits.
- All subjects have discontinued from the study.
- The IRB, FDA, LCI DSMC, Sponsor-Investigator or Merck discontinues the study because of safety considerations.
- The Sponsor-Investigator defines an administrative or clinical cut-off date.

13.2. Termination

The study will be terminated when one or more of the following conditions occur:

If risk-benefit ratio becomes unacceptable owing to, for example:

- Safety findings from this study (e.g. SAEs)
- Results of any interim analysis
- Results of parallel clinical studies
- Results of parallel animal studies (e.g. toxicity, teratogenicity, carcinogenicity or reproduction toxicity).
- If the study conduct (e.g. recruitment rate; drop-out rate; data quality; protocol compliance) does not suggest a proper completion of the trial within a reasonable time frame.

The Sponsor-Investigator has the right to close the trial at any site and at any time. For any of the above closures, the following applies:

- Closures should occur only after consultation between involved parties.
- All affected institutions must be informed as applicable according to local law.
- In case of a partial study closure, ongoing subjects, including those in follow-up, must be taken care of in an ethical manner.

Details for individual subject's withdrawal can be found in Section 4.3.3.

